# 6. Study Objectives and Design

## 6.1. Study Objectives

This research aims to elucidate LiOr's plausibility, at a known safe dose, over an extended period in a preliminary study. This is a feasibility study comprising the preliminary work required prior to formal trials examining commercially available LiOr supplementation for DMF. No specific hypotheses are therefore proposed. In this open label study, people who constitute a target population for LiOR will be invited to take commercially available LiOr for up to six months to establish its plausibility as a putative intervention for trials. The specific objectives are to investigate up to six months of open-label 20mg daily LiOr to identify its within-subjects effects on the following as co-primary outcomes:

1. The potential to examine bioavailability of LiOr (i.e. whether lithium is present at detectable levels in the serum using a standard laboratory lithium test), assessing lithium levels in serum.

2. The acceptability of 20mg daily LiOr over 6 months (assessed by self-report adherence and discontinuation rates) to inform a future study design.

3. Description of any positive and/or negative experiences of 20mg daily LiOr over 6 months (assessed via participant-report) to inform a future study design.

4. The feasibility of the protocol including intervention delivery and assessment visits (including assessments mentioned above, plus putative primary (mood) and secondary (functioning, cognition) outcome measures and assessment of potential confounders). Overall feasibility will be assessed via missing data and study withdrawal rates.

An exploratory analysis of change will be undertaken as secondary objectives for measures over time to inform a future definitive study design:

1. LiOR's biological effects, through assessment of key candidate blood-based biomarkers, namely neuroprotective growth factors (BDNF, VEGF) and inflammatory cytokines (IL-6, TNFa, IL-1b, IL-8, CRP) between week 0 and week 26.

2. LiOr's effects on mood, through assessing changes in mood ratings between week 0 and week 26.

3. LiOr's effects on cognition and functioning, through assessing changes in cognitive and psychosocial function between week 0 and week 26.

These aims will be met via within-subjects comparisons for each timepoint relative to baseline (weeks 2, 4, 8, 16, 26).

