#### 6.2. Study Design

A single site, one arm unblinded open label study investigating the effects of LiOr supplementation (20mg, once per day) for up to six months. We will recruit 40 people for this feasibility study.

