#### W2: Intermediary assessment:

- Blood test (repeat from baseline)
- Cognitive test (repeat from baseline)
- Wellbeing measures (repeat from baseline)
- Adherence: Tablets Routine Questionnaire (TRQ) [all remaining timepoints]
- Subjective effects of LiOR: Lithium Side Effects Rating Scale (LiSERS) modified to bolster both positive and negative effects of lithium [all remaining timepoints]

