## 12.1. Sample Size

As an initial feasibility study, a sample size calculation is not warranted. However, a sample of 40 participants permits estimation of a 50% dropout rate to within a 95% confidence interval of +/-15%.[Research Design Service. NIHR. Available at: https://www.rds-london.nihr.ac.uk/resources/justify-sample-size-for-a-feasibility-study/]. The existence of six repeated measures and focus on within-subjects change/variability will help boost power to observe effects without aiming to determine statistical significance of effects with any precision.

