## 12.2. Analysis

Intention-to-treat analyses will be undertaken. In a few cases, a sensitivity analysis will be carried out, excluding non-adherent participants (these are specified below, where this applies).

Final analyses will be conducted after data collection has been completed and data cleaned. However, it is worth noting that an interim analysis is planned in May 2025 for all primary analyses below. This is for the purpose of initial pilot data to be included in funding applications being submitted for a feasibility study. No changes to the protocol or any procedures will be made based on this.

Variables will be summarised using descriptive statistics (i.e., mean and standard deviation [SD] or median and interquartile range [IQR] or frequencies and proportions, as appropriate).

Analyses pertaining to each outcome are listed below:

1. LiOR bioavailability as assessed by lithium levels in serum. This will be analysed descriptively, as above. Intraand inter- participant variation will be calculated. Overall changes over time may be assessed using a repeatedmeasures ANOVA (including only adherent participants taking a stable dose) to inform a potential future trial design.

2. LiOR acceptability as assessed by adherence rates (TRQ) and discontinuation. Rates of adherence (< 20% missed) will be assessed descriptively for each timepoint, and extent of adherence will also be described as a continuous (total TRQ score) measure. Rates of discontinuation (participant-report) will be described. Continuous adherence scores (for participants not discontinuing LiOR) over time will be tentatively compared using a repeated-measures ANOVA to inform a potential future trial design.

3. Subjective experiences of LiOR: negative experiences will be described via continuous LiSERS score measure, and positive experiences will be reported as participant-reported rates (yes/no to those listed). LiSERS scores over time (adherent participants only) will be compared using a repeated-measures ANOVA (possibly including dose as a between-subjects factor, pending dose variation within and between participants) to inform a potential future trial design.

4. Protocol feasibility as assessed by the rates (assessed descriptively) of attrition from the study, and of visits missed, and specific data for the putative primary outcomes i.e., mood measures.

There are three secondary outcomes, analysed as exploratory indications of change to inform a future definitive study design:

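### Co-primary outcome 3 reports positive experiences effect by effect but negative experiences only as a continuous LiSERS score, so the planned summary does not show which negative effects occurred or in how many participants

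*Protocol*

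**What the plan says.** Section 6.1 of the protocol sets the third co-primary objective as "Description of any positive and/or negative experiences of 20mg daily LiOr over 6 months (assessed via participant-report) to inform a future study design". The synopsis has an equivalent objective.

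Section 12.2, primary outcome 3, then assigns a different summary to each side: "negative experiences will be described via continuous LiSERS score measure, and positive experiences will be reported as participant-reported rates (yes/no to those listed"). A repeated-measures ANOVA of LiSERS scores over time follows, in adherent participants only, possibly with dose as a factor.

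The instrument is introduced under the week 2 visit in section 10.1. There the LiSERS is described as "modified to bolster both positive and negative effects of lithium", so content was strengthened on both sides. It is given at weeks 2, 4, 8, 16 and 26. The form and its scoring are not reproduced.

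Three other passages bear on the point:

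- Section 12.2 opens with a general rule that variables are summarised by mean and SD, median and IQR, or frequencies and proportions, as suits the variable. It also plans an interim analysis of all primary analyses in May 2025, to supply pilot data for funding applications.
- Section 11.1 states that safety is not a study outcome.
- Sections 11.3 and 11.4 have adverse events asked about at each visit and documented events included in the primary report. All events classed as adverse reactions are recorded. Other events are exempt from reporting where no action is needed or they are unrelated to the study or supplement.

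**The concern.** The objective is descriptive: what do people taking the supplement notice, good and bad? The plan answers this by name and frequency for the good and by a scale score for the bad. A score indicates overall burden. It cannot be turned back into a list of effects with a count against each, and that list is what the next study needs for its participant information, its side-effect checklist and its expected event rates.

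The asymmetry also affects how the results read. Itemised benefits would stand beside a single harm figure in the final report and, earlier, in the interim results prepared for funding applications. The two sides could not be compared on a common scale.

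**Working it through.** **1. The protocol's only precision figure.** Section 6.2: "We will recruit 40 people for this feasibility study". Section 12.1: "a sample of 40 participants permits estimation of a 50% dropout rate to within a 95% confidence interval of +/-15" percentage points. Check: 1.96 × √(0.5 × 0.5 / 40) = 1.96 × 0.0791 = 0.155, or 15.5 points. The Wilson half-width is 14.8 points. The stated figure reproduces. It does not depend on how outcome 3 is summarised, but it shows that the protocol regards proportions at N = 40 as worth estimating.

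**2. What summaries of a score can and cannot show.** The form is not shown, so the scores below are assumptions for illustration.

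*Same mean, different spread.* Cohort A: 40 people score 2 each. Cohort B: 4 people score 20 and 36 score 0.

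- Mean: A = 80/40 = 2.0; B = 80/40 = 2.0.
- Any negative effect: A = 100%; B = 10%.
- SD: A = 0; B = √[(4 × 18² + 36 × 2²)/39] = √(1440/39) ≈ 6.1.
- Median: A = 2; B = 0.

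The mean alone does not separate these cohorts, but the SD or the median does, and the protocol provides for both. Spread is therefore not lost.

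*Same distribution, different effects.* Cohort C: all 40 people score one point on the same item. Cohort D: all 40 score one point, spread over ten items with four people on each.

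- Every score is 1, so the mean is 1, the SD 0 and the median 1 in both cohorts.
- Rate per effect: C = 40/40 = 100% for one effect; D = 4/40 = 10% for each of ten effects.

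No summary of the score separates C from D. This is the information that the planned summary leaves out.

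**3. Whether per-effect rates are usable at this size.** Exact (Clopper–Pearson) 95% intervals for one negative effect at N = 40:

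| Reporting the effect | 95% interval |
|---|---|
| 0/40 | 0% to 8.8% |
| 4/40 | 2.8% to 23.7% |
| 10/40 | 12.7% to 41.2% |
| 20/40 | 33.8% to 66.2% |

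If only 30 or 20 people answer (assumed, to allow for attrition), the upper limit for no reports is 11.6% or 16.8%. With the same denominator, these rates are as estimable as the positive-effect rates already planned.

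**4. Comparison within section 12.2.** Outcome 2 describes adherence both as a rate and as a continuous score. Outcome 3 gives positive experiences rates and negative experiences only a score.

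**The case against.** The strongest case against has four parts.

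*The general descriptive rule already allows frequencies.* It does, and the item responses would presumably be held, so nothing is irrecoverable. But outcome 3 is the specific instruction, and it assigns the score to negative experiences and rates to positive ones. Followed as written, it produces no count per negative effect.

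*Adverse-event recording fills the gap.* In part. All adverse reactions are recorded without a severity threshold, so mild effects attributed to the supplement are captured. What can fall outside is the mild complaint that needs no action and is not attributed to the supplement. That attribution is the investigator's judgement in a study without a control group. A participant-reported scale does not depend on it.

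*A reader might infer that benefits are summed into the harm score*, because the form covers both directions and the ANOVA refers only to LiSERS scores. The documents do not support this. The preceding sentence in section 12.2 separates negative experiences (score) from positive ones (yes/no rates), and scoring detail may sit in a statistical analysis plan that is not shown. No size can be put on an error that the text does not describe. What remains is a term that one phrase would make unambiguous.

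*This is table-shell detail.* An unstated table would be. Here the protocol states the summary for a co-primary outcome, and the summary fits the objective poorly.

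It would also be too strong to say that severe effects in a few people would be hidden: the SD or median would reveal them, as shown in the working.

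**Conclusion.** The point holds as a mismatch between a co-primary objective and its stated summary. The plan describes positive experiences by effect and frequency but negative experiences only by a continuous score, which does not identify the effects or count the people who had them. Adverse-event reporting narrows the gap without closing it.

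The consequence is for the usefulness and balance of the report, including the interim one. No sample size, precision figure or test changes. The illustrations assume item scores, because the form is not shown; the conclusion needs only that the score combines more than one negative item. The documents do not show that positive items enter the score, and that is not part of this conclusion. The change is worth making because it is cheap and the data should already be there.

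**What to change.** In section 12.2, outcome 3:

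1. Keep the LiSERS score and add, for each negative item, the number and percentage of participants reporting it, with severity where the form grades it. Give this at each visit and as 'ever', in the same form and with the same denominator as the positive items. State that denominator at each visit, because the synopsis does not require participants who discontinue the supplement to attend intermediary visits.
2. As a clarification of wording only, state that the LiSERS score, including the one used in the repeated-measures comparison, is computed from the negative items.

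Apply both to the interim and the final analysis. The cost is two sentences and one extra descriptive table from an instrument already given at weeks 2 to 26. The number of participants, the visits and the data collected stay as they are.

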Endpoints:	Week 0: Baseline assessment, pre-intervention	
	Week 2, 4, 8, 16: Intermediary follow-up assessments Week 26: Final follow-up assessment	
Sample Size:	40 individuals.	

Summary Of Eligibility Criteria:	Aged between 18-65 at study entry. Meet DSM-5 criteria for a current depressive episode and exceed thresholds indicating presence of mixed features. Undergoing antidepressant treatment (stable intervention/dose unchanged for >6 weeks). No diagnosis of bipolar disorder received. No other severely impairing health condition. No contraindications to lithium treatment (including currently taking lithium). No significant suicidality.		
Intervention (Description, frequency, details of delivery):	Open label lithium orotate supplement as available commercially, 20mg once per day. Participants will be instructed to begin taking the supplement the day after the baseline assessment for a period of up to six months. If participants prefer to move to a lower dose, they can titrate down to 15mg, 10mg or 5mg. Intervention is self-managed, but participants are provided with information about the supplement and have access to the research team to answer any questions or provide further information. Participants who discontinue will remain in the study, although will not be required to attend intermediary follow- up visits, which collect information related to the intervention. We will ask them to attend the final endpoint visit, however.		
Comparator Intervention:	n/a		
Maximum Duration Of Treatment Of A Participant:	6 months / 26 weeks (i.e., from baseline up until the final follow-up assessment). Participants are permitted to discontinue the supplement at any time they wish.		
Version And Date Of Final Protocol:	[to be completed]		
Version And Date Of Protocol Amendments:	n/a as yet		

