#### 11.3. Procedures for Recording and Reporting Adverse Events

Any adverse events will be recorded by a researcher at each visit asking participants if they have had any troubles and record these systematically. Even though LiOR is not a medicinal product, the standard definitions provided by The Medicines for Human Use (Clinical Trials) Regulations 2004 and Amended Regulations 2006 with regards to adverse events will be used, as follows:

Adverse Event (AE): Any untoward medical occurrence in a subject to whom an intervention has been administered including occurrences which are not necessarily caused by or related to that intervention.

Adverse Reaction (AR): Any untoward and unintended response in a subject to an intervention which is related to the intervention administration to that subject.

Unexpected Adverse Reaction (UAR): An adverse reaction the nature and severity of which is not consistent with the information about the intervention in question.

Serious Adverse Event (SAE), Serious Adverse Reaction (SAR) or Suspected Unexpected Serious Adverse Reaction (SUSAR): Any adverse event, adverse reaction or unexpected adverse reaction, respectively, that: results in death; is life-threatening; required hospitalisation or prolongation of existing hospitalisation; results in persistent or significant disability or incapacity; consists of a congenital anomaly or birth defect.

Important Medical Events (IME): Events that may not be immediately life-threatening or result in death or hospitalisation but may jeopardise the patient or may require an intervention to prevent one of the other outcomes listed in the definition above should also be considered serious.

Any AEs (excepting those specified in this protocol as not requiring reporting; see below section 11.4) that occur throughout the duration of the study will be recorded in the participant case report form. Investigators will assess whether the AE may be related to study participation and will also assess the severity of the event. Documented AEs reported after a participant signs the consent form will be included in the primary study report.

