#### 11.4. Adverse events that do not require reporting

No SAEs are expected in this study. Therefore, any SAEs will be reported as will ARs, UARs, SARs or SUSARs or IMEs. AEs that do not meet the above criteria but require intervention (e.g., safety concerns communicated to healthcare professional or incidence of acute episode requiring changes to treatment regime) will be reported. Other AEs do not require reporting (e.g., mild distress disclosed by participants where no further action is required or unrelated to the study/LiOR).

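### The LiSERS comparison over time is planned in adherent participants only, against the protocol's own intention-to-treat rule, and probably understates negative experiences

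*Protocol*

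**What the plan says.** Objective 3 in Section 6.1, one of four co-primary objectives, is "Description of any positive and/or negative experiences of 20mg daily LiOr over 6 months (assessed via participant-report"). Section 12.2, item 3, serves it in two steps. Negative experiences are first described by the continuous LiSERS score, with no stated restriction on who is included. Then "LiSERS scores over time (adherent participants only) will be compared using a repeated-measures ANOVA", with dose considered as a factor: "possibly including dose as a between-subjects factor, pending dose variation within and between participants".

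Section 12.2 opens by adopting intention-to-treat and says that in a few cases a sensitivity analysis will leave out non-adherent participants. Each of the three secondary outcomes gets a repeated-measures ANOVA by intention-to-treat plus an adherent-only sensitivity analysis.

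Four other places bear on the point:

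- Table 1 (Section 6.3) schedules LiSERS at weeks 2, 4, 8, 16 and 26, with none at baseline.
- Section 7.3 defines adherence by a Tablets Routine Questionnaire (TRQ) score equating to 80%.
- The Synopsis says: "Participants who discontinue will remain in the study, although will not be required to attend intermediary" visits, although they are asked to come at week 26.
- The Synopsis and Section 7.1 let participants lower their own dose during the study.

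**The concern.** Negative effects are an obvious reason to miss capsules, cut down or stop. A comparison confined to adherent participants therefore selects on something that the outcome itself can cause, and the people most likely to be left out are those with the worse scores. If burden and non-adherence are positively related, the adherent-only mean lies below the mean for everyone who took LiOr.

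The dose factor has a related weakness. Dose is chosen by the participant and can change within a person, so a between-subjects contrast would mix any effect of dose with the effect of tolerability on dose.

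At stake is the tolerability information meant to shape the next study. Section 12.2 also schedules an interim look at all primary analyses in May 2025 to supply pilot data for funding applications, so a favourable distortion would be used early.

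**Working it through.** **1. The plan's own figure.** The only precision statement is in Section 12.1: "a sample of 40 participants permits estimation of a 50% dropout rate to within a 95% confidence interval of +/-15" per cent. The half-width is 1.96 × √(0.5 × 0.5 / 40) = 0.155, so the figure reproduces after rounding. It is not in dispute. It matters here only because it names 50% dropout as a planning scenario for 40 participants.

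**2. The analyses side by side (Section 12.2).**

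| Outcome | All-participant version | Adherent-only version |
|---|---|---|
| LiSERS, description | no restriction stated | none |
| LiSERS, comparison over time | none | the only one |
| Biomarkers, mood, cognition and function | yes | sensitivity analysis |

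The over-time LiSERS comparison is out of line with the section's opening rule and with every secondary outcome.

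**3. Size of the selection effect at one time point.** These assumptions are not in the protocol: burden is standard normal, a fraction d with the highest propensity to be non-adherent is excluded, and that propensity correlates r with burden. The retained mean then falls by r × φ(c) / (1 − d), where c = Φ⁻¹(1 − d).

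- d = 0.20 (32 of 40 left): φ(0.842) / 0.8 = 0.280 / 0.8 = 0.350. The shift is 0.105, 0.175 and 0.245 SD for r = 0.3, 0.5 and 0.7.
- d = 0.50 (20 left): φ(0) / 0.5 = 0.399 / 0.5 = 0.798. The shift is 0.24, 0.40 and 0.56 SD.
- r = 0: no shift.

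**4. Shape over time.** This is a second illustration, again on assumed inputs. Score = 0.7 × person effect + 0.71 × noise (SD 1, true mean 0 at all five visits), and the log-odds of stopping after a visit are −2.2 + score, which gives about 13% at the first visit. Simulated with 1,000,000 people:

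| | W2 | W4 | W8 | W16 | W26 |
|---|---|---|---|---|---|
| Still taking LiOr | 100% | 87% | 76% | 66% | 59% |
| Mean among those still taking it (SD) | 0.00 | −0.06 | −0.11 | −0.16 | −0.2 |
| Mean among those taking it at all five visits (SD) | −0.26 | −0.26 | −0.26 | −0.26 | −0.2 |

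A standard repeated-measures ANOVA needs all visits, so the last row is the relevant one. It shows a level that is too low by 0.2 to 0.26 SD and almost flat. For scale, the standard error of a mean from 40 people is 1/√40 = 0.16 SD. With 0.59 × 40 ≈ 24 complete cases it is 1/√24 = 0.20 SD.

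**5. What the unrestricted description can still see.** Scores before stopping remain, and so does a week 26 score if the participant attends. Between the two there may be nothing, and the week 26 score is taken off the supplement. Someone who stops before week 2 may give no score while taking LiOr.

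**The case against.** The strongest reply is that the co-primary objective is a description, and that description carries no adherence restriction. The ANOVA is an addition meant to inform a later design, in a study that proposes no hypotheses. Scores before stopping, week 26 scores and discontinuation rates (item 2) are all kept, and Section 9.6 promises efforts to continue follow-up. This stands. A reader might infer that those harmed enough to stop are filtered out of the co-primary result. The text does not support that, because the restriction attaches only to the over-time comparison.

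Three other strong readings also go too far.

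- **A spurious improvement over time.** The falling means in step 4 describe whoever is still taking LiOr at each visit. They do not describe the planned complete-case test, where the same model gives a level shift.
- **Lower doses will look worse.** The protocol says only that participants may reduce if they wish, and the dose factor is conditional. Confounding is clear; its direction is conjecture.
- **Mild adverse events go unrecorded.** Section 11.3 says "Any adverse events will be recorded by a researcher at each visit asking participants if they have had any troubles", later exempts Section 11.4 events from the case report form, and Section 11.4 says "Other AEs do not require reporting (e.g., mild distress disclosed by participants where no further action is required or unrelated to the study/LiOR"). That is a conflict of wording, not a settled rule of non-recording. Adverse reactions, serious events and events needing intervention are still captured. LiSERS is also collected separately from adverse event forms.

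It can also be said that adherent-only scores show experience while actually taking LiOr. That is a reasonable secondary question, but it does not need the 80% cut, which also removes people who took part of their capsules and felt unwell on them.

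**Conclusion.** The point holds in a limited form. The over-time LiSERS comparison contradicts the section's own rule, has no all-participant counterpart, and conditions on a post-baseline variable that side effects can influence. It probably understates the level of negative experiences among all who took LiOr.

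The direction rests on one assumption, that worse experiences make non-adherence more likely. The size cannot be determined from the protocol: the illustrations run from 0.1 to 0.56 SD across the inputs in step 3, and from 0.2 to 0.26 SD in the complete-case model. These describe stopping or exclusion in general and do not model the TRQ threshold itself.

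The dose factor is unsound as a between-subjects term if it is used. The gap in scores after stopping is a possible loss, not a certain one, since attendance is not required but also not ruled out. The adverse event wording is a separate, minor matter.

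**What to change.** In Section 12.2, item 3:

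- Make the main over-time LiSERS comparison one in all participants who took LiOr, using every observed score (for example a mixed model). Keep adherent-only as the sensitivity analysis, as for the secondary outcomes. In the model of step 4, stopping depends only on scores already observed, so a correctly specified mixed model would use that information. It would not cover worsening that occurs between visits.
- For that reason, tabulate the last LiSERS before each stop or dose reduction and, where feasible, obtain one LiSERS by phone when a participant stops.
- Drop dose as a between-subjects factor. Show dose at each visit descriptively, including none, so that scores off the supplement can be told apart.

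Separately, reconcile the two statements in Section 11.3 with each other and with Section 11.4, making clear what is recorded and what is reported onward.

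The cost is slightly more analysis and a short phone contact for each participant who stops. The tolerability picture may look less favourable than under the present wording.

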#### 7.3. Intervention adherence

Adherence will be examined via completion of the participant-reported, validated Tablets Routine Questionnaire. A TRQ score equating to 80% adherence is a conservative threshold for dichotomous adherence definition. (see Section 10 for more details).

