1. LiOR's biological effects, through assessment of key candidate blood-based biomarkers, namely neuroprotective growth factors (BDNF, VEGF) and inflammatory cytokines (IL-6, TNFa, IL-1b, IL-8, CRP) throughout the study. This will be examined using a repeated-measures ANOVA according to the intention-to-treat principle, with a sensitivity analysis to examine only adherent participants.

2. LiOr's effects on mood, through assessing changes in mood ratings (M3VAS, ISS, IDS, YMRS) throughout the study. These will be examined using a repeated-measures ANOVA according to the intention-to-treat principle, with a sensitivity analysis to examine only adherent participants.

3. LiOr's effects on cognition and psychosocial function, through assessing changes in THINC-IT and FAST scores respectively, throughout the study. These will be examined using a repeated-measures ANOVA according to the intention-to-treat principle, with a sensitivity analysis to examine only adherent participants.

Ancillary exploratory analyses will examine other wellbeing outcomes (e.g., EQ5D), service use, and a potential impact of bipolar features on outcomes during the study. Additional exploratory analyses using the data collected may be conducted.

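### The only planned comparison of LiSERS over time excludes non-adherent participants, so it can understate the level of negative effects and mask part of a real worsening

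*Protocol*

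**What the plan says.** Co-primary objective 3 (Section 6.1) is "Description of any positive and/or negative experiences of 20mg daily LiOr over 6 months", by participant report and in order to inform a future design.

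Section 12.2 opens with a general rule: "Intention-to-treat analyses will be undertaken. In a few cases, a sensitivity analysis will be carried out, excluding non-adherent participants".

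Item 3 of the same section then plans two things for LiSERS:

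- A description: "negative experiences will be described via continuous LiSERS score measure". No adherence limit is attached.
- A comparison over time: "LiSERS scores over time (adherent participants only) will be compared using a repeated-measures ANOVA", possibly with dose as a between-subjects factor. It is not called a sensitivity analysis.

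For each of the three secondary outcomes, Section 12.2 instead plans a "repeated-measures ANOVA according to the intention-to-treat principle, with a sensitivity analysis to examine only adherent participants".

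Adherence comes from the TRQ. Section 7.3 says "A TRQ score equating to 80% adherence is a conservative threshold for dichotomous adherence definition", and Section 12.2 describes adherence rates (less than 20% missed) at each timepoint. TRQ and LiSERS are both collected at W2, W4, W8, W16 and W26 (Sections 6.3 and 10.1). The protocol does not say whether the adherent set for item 3 is fixed for the whole study or redrawn at each visit.

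**The concern.** Missing capsules is one natural response to unpleasant effects. Adherence is measured after LiOr starts, so it may be a consequence of the outcome that item 3 measures. Selecting on it can preferentially remove people with high LiSERS scores. Their scores are collected while they keep attending, but they do not enter the one comparison that speaks to how negative effects develop over six months.

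Item 1 also restricts its serum lithium comparison to adherent participants on a stable dose. That is easier to defend, because serum lithium directly reflects intake. The reason does not carry over to reported side effects.

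What is at stake is the tolerability picture passed to the next study. Section 11.1 says safety is not an outcome, so LiSERS is the main quantitative measure of negative effects. Section 12.2 also plans an interim run of all primary analyses to support funding applications, so a flattering pattern could be used early.

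**Working it through.** **Internal consistency.** Set side by side, the opening rule of Section 12.2 and the three secondary outcomes put intention-to-treat first and adherent-only second. Item 3 has adherent-only alone. This is a stated choice, not a detail left open.

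**The plan's own figure.** The protocol gives no number on this point. Its one design figure, a 95% interval of ±15 points for a 50% dropout rate with 40 people, is 1.96 × √(0.5 × 0.5 / 40) = 0.155. Nothing below depends on it.

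**Hand check of the mechanism (all inputs assumed).** Suppose 30% tolerate LiOr badly, 60% of them fall below the adherence threshold, and everyone else adheres. Bad tolerators among adherers are then 0.30 × 0.40 / (1 − 0.30 × 0.60) = 0.12 / 0.82 = 14.6%. The adherent-only mean shows 14.6 / 30 = 49% of the true excess score. With 20–40% bad tolerators and 40–80% of them non-adherent, the range is 24–71%.

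**Simulation with no true change.** 20,000 studies of 40 people with five LiSERS visits.

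- Score: y = u + e, with mean 0, SD 1 and within-person correlation 0.6 (assumed).
- Non-adherence at a visit: logit P = logit(b) + ln(OR) × y, with b = 10% or 20% and OR = 1, 2 or 3 per SD (assumed).
- In the full set the mean is 0 at every visit by construction.

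The columns give the mildest and strongest links, in SD units.

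| Reading of the adherent set | b = 10%, OR 2 | b = 20%, OR 3 | Pattern over visits |
|---|---|---|---|
| Adherent at every visit | −0.24 | −0.57 | Flat; 56% and 31% of people kept |
| Adherent at most visits | −0.02 | −0.15 | Flat |
| Adherent at last visit | −0.05, then −0.08 at W26 | about −0.13, then −0.22 at W26 | Small false improvement |
| Per visit, may return | −0.08 | −0.22 | Flat |
| Per visit, no return | −0.08 at W2 to −0.24 at W26 | −0.22 at W2 to −0.57 at W26 | False improvement of 0.16 and 0.35 |

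With OR = 1 the bias is zero under every reading. The ANOVA's false-positive rate is about 5% in the set adherent at every visit, and 5.4% to 8.2% in the set adherent at the last visit.

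A standard repeated-measures ANOVA uses only people with every visit, so a per-visit adherent set would in practice become the first row. For 40 people that is 0.56 × 40 ≈ 22 down to 0.31 × 40 ≈ 12.

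**Simulation with a real worsening.** Same model, but 30% of people worsen by 1.5 SD in a straight line from W2 to W26, a true mean rise of 0.30 × 1.5 = 0.45 SD. In the set adherent at every visit the rise appears as 0.34 SD (b = 10%, OR 2) or 0.21 SD (b = 20%, OR 3). If everyone worsens equally by 0.45 SD, the same set shows 0.44 and 0.42 SD. The masking therefore needs worsening to be concentrated in some people.

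**The case against.** The best defence is that objective 3 asks for a description, and the description in item 3 carries no adherence limit. A reader might infer that harm data from non-adherers are thrown away, or that negative effects will be understated in everything reported. The text does not support that. Their scores stay in the descriptive result. Tolerability also shows in the adherence and discontinuation rates, the recorded doses taken, and the adverse events asked about at each visit. This stands, and it confines the point to the comparison over time.

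A reader might also infer that LiSERS will falsely appear to improve. That is not shown for the most natural form of the planned method. A complete-case ANOVA on people adherent throughout is flat under no change, with the usual false-positive rate. A false trend needs a set that shrinks with no return, or one defined by late adherence, and the protocol specifies neither. This also stands. It does not rescue the analysis, because the level in that set is still too low and an uneven worsening is still partly hidden.

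Three further points limit the weight. Every magnitude input is assumed. Section 7.1 lets participants take fewer capsules, which gives poor tolerators an alternative to skipping and may weaken the link. The ANOVA is exploratory in a feasibility study with no hypotheses, and restricting an exposure-dependent measure to people taking the product is a recognisable choice. It is acceptable as a secondary view, but not as the only one.

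**Conclusion.** The point holds for the comparison of LiSERS over time. It departs from the section's own intention-to-treat rule and from the order used for every secondary outcome, and it conditions on a variable measured after LiOr starts that side effects may influence.

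The likely direction is towards fewer apparent negative effects. The size is not known from the protocol: about 0.02 to 0.57 SD under the assumed links, and zero if adherence and side effects are unrelated. Masking of a real worsening ranges from almost none, when it is shared equally, to about half in the strongest uneven case (0.21 of 0.45 SD). The analysis is exploratory, so this is a correction that should be made but does not threaten the study.

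**What to change.** In Section 12.2, item 3:

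1. Make the main comparison use all available LiSERS scores from all participants, whatever the TRQ score, including the W26 score of those who discontinued. Use a method that keeps people with missing visits, such as a mixed model for repeated measures.
2. Make the adherent-only comparison the sensitivity analysis, and state whether adherence is judged per visit or over the whole study.
3. Tabulate LiSERS by adherence status (less than 20% missed, or not) at each visit.

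Limiting the main set to people who took some LiOr since the previous visit would not do. That is an on-treatment set, and it would again drop people who stopped because of side effects.

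The cost is a little more analysis work and a possibly less favourable tolerability figure; no new data are needed. One gap remains. The synopsis does not require intermediary visits from people who discontinue, so most of those scores will be missing. The mixed model then rests on earlier scores accounting for the missingness. The report should state this as a limitation.
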